4.3 Withdrawal of Subjects from the Study

A good faith effort will be made to ensure that subjects complete the study through the 6-month assessments, consistent with the provisions of informed consent and good clinical judgment with respect to safety. The following are potential reasons to terminate the participation of a subject in the study:

- The subject's health would be jeopardized by continued participation.
- Lost to follow-up: subject fails to return to the study site for scheduled visits and does not respond to multiple telephone or written attempts to contact. (Note: if subject cannot return to the study site due to relocation, but moves to an area near another participating site, all efforts should be made to continue study participation at that site).
- Withdrawal of consent: subject or the subject's legally authorized representative or legally acceptable representative (LAR), as applicable in the region where the study is conducted, decides to stop participation in the study for any reason other than an AE, or is unable to complete the study as described in the study protocol. Although a subject or LAR is not obliged to give his/her reason for withdrawing prematurely, the Investigator will make a reasonable effort to obtain the reason while fully respecting the subject's rights. Every effort will be made to contact a subject or LAR who fails to attend any follow-up appointments/contacts in order to complete study assessments.
- Administrative: the Sponsor decides to terminate or discontinue the study (either at the study site or the entire study).

The reason for withdrawal will be captured on the appropriate electronic case report form (eCRF). The Study Termination form must be completed for all randomized subjects, including subjects discontinuing prior to any study drug administration. The Medical Monitor will be informed of early withdrawal of a subject from the study.

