Subjects without a GOS response assessment at Month 6 but who have a death date from the Death Report eCRF within 6 months + 28 days of their randomization date (calculated as death date – randomization date + 1 \leq 208) will be assigned a Month 6 GOS response of Dead. Similarly, subjects without a GOS response assessment at Month 3 but who have a death date from the Death Report eCRF within 3 months + 28 days of their randomization date (calculated as death date – randomization date + 1 \leq 118) will be assigned a Month 3 GOS response of Dead.

Secondary Endpoint: Mortality at Month 1

Survival status from the date of injury (Day 1 of the study) until Day 30 (Month 1) will be monitored and recorded as lost to follow-up, consent withdrawn, alive, dead or other. Only subjects with a mortality assessment post-injury of alive or dead will be used in the assessment of mortality.

Secondary Endpoint: Mortality at Month 6

Survival status from the date of injury (Day 1 of the study) until Day 180 (Month 6) will be monitored and recorded as lost to follow-up, consent withdrawn, alive, dead or other. Only subjects with a mortality assessment post-injury of alive or dead will be used in the assessment of mortality.

Time to death

The time to death (in days) will be defined as:

$$\text{Date of death} - \text{date of TBI} + 1$$

If a subject does not die during the conduct of the study, they will be censored at the earliest (minimum) of their Month 6 GOS assessment date and end of study date, and censor time (in days) will be defined as:

$$\text{Minimum(month 6 GOS assessment date, end of study date)} - \text{date of TBI} + 1$$

Since subjects were not followed for death after their Month 6 GOS assessment, subjects who have a death recorded after the assessment will be censored on the date of their Month 6 assessment.

Exploratory Endpoint: CPP

The following formulae are used to derive CPP:

$$\text{Mean Arterial Pressure (MAP)} = \frac{2}{3} \text{ diastolic BP} + \frac{1}{3} \text{ systolic BP};$$

$$\text{CPP} = \text{MAP} - \text{ICP}.$$

MAP will be recorded as missing if either systolic BP and/or diastolic BP measurements are not recorded. CPP will be calculated where MAP and ICP have both been recorded; if either is missing the CPP will be recorded as missing.

Exploratory Endpoint: TIL

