9.5.3 Exploratory Variables

9.5.3.1 Time to Death

The actual time to death will be analyzed for the mITT population.

If a subject does not die during the conduct of the study, they will be censored at their Month 6 GOS assessment or end of study date, whichever comes first.

The LIFETEST procedure in SAS® will be used to produce Kaplan-Meier plots and estimates of 25th, 50th, and 75th quartiles and corresponding 95% confidence limits of the median time to death. The 2 treatment groups will be compared using a 2-sided log-rank test. Examination of the point estimates will indicate the direction of the treatment difference. The cumulative percent mortality based on the Kaplan-Meier survival probability estimates will be plotted for each treatment group.

The time to death (in days) will be further analyzed using a Cox proportional hazard model. The comparison of the treatment effect on the time to death will be based on the hazard ratio (HR) from the Cox regression model using the PHREG procedure in SAS®. Estimates of HR and 95% confidence limits will be presented. The model will include the same terms as the primary efficacy analysis, namely treatment, region, age, GCS motor score, pupil response, and CT classification.

The Cox proportional hazards model is a standard model used in failure time analysis. Compared to parametric analyses, its assumptions are fairly unspecified and will therefore yield robust estimates of the treatment effect. The model will be applied using the Efron approach for handling ties, since this approach is known to give a reasonable approximation of the exact likelihood in the presence of ties and is computationally faster when large amounts of data are being analyzed.

9.5.3.2 Comparison of CT scans at admission and Day 6

A CT scan will be performed before randomization (Day 1) and once again at Day 6 ± 1 day post-injury to assess the progression of lesion volume and brain edema. The findings by the Central Reader will be classified in accordance with the Marshall classification:

- Diffuse injury I - no visible pathology (CT class I),
- Diffuse injury II (CT class II),
- Diffuse injury III – swelling (CT class III),
- Diffuse injury IV – shift (CT class IV),
- Evacuated mass lesion (CT class V),
- Non-evacuated mass lesion (CT class VI).

A shift summary of CT classification from Baseline to Day 6 will be presented by treatment group.

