 [Update the footnotes to reflect Month 1 timepoint.]

Table 14.2.5.3 Summary and Analysis of Mortality at Month 6 (PP Population)

Table 14.2.5.4 Summary and Analysis of Mortality at Month 1 (PP Population)

Table 14.2.5.5 Summary and Kaplan-Meier Analysis of Time to Death¹ (days) (mITT Population)

	Statistic	BHR-100 (N=xx)	Placebo (N=xx)
Kaplan-Meier Estimates			
	Total Deaths	xx	xx
	Total Censored	xx	xx
	25 th percentile	xx	xx
	Median (95% CI)	xx (xx , xx)	xx (xx , xx)
	75 th percentile	xx	xx
Treatment Difference from Placebo ²		p=0.xxx	

¹ Time to Death (in days) = Date of death/date of last contact (for censored records) - date of TBI + 1.

² P-value is based on Log-Rank test.

Source: Listing 16.2.6.3.1.

Program: xxxxxxx.sas, Output: xxxxxxx.rtf, Generated on: DDMONYYYY xx:xx, Page x of x

[Note to Programmer: The K-M estimates are those obtained from PROC LIFETEST.

The log-rank test is fitted in SAS using the following syntax:

```
PROC LIFETEST DATA=<dataset name>;
  TIME WKS*CENS(1 - censoring indicator);
  STRATA TREATMENT;
RUN; ]
```

Table 14.2.5.6 Summary of Cox Proportional Hazards Analysis of Time to Death (days) (mITT Population)

Factor/Covariate ¹	Hazard Ratio ¹	95% Confidence Limits	P-value
Treatment Group (BHR-100 vs. Placebo)	x.xxx	(x.xxxx, x.xxxx)	0.xxx
Region (North America vs. Europe)	x.xxx	(x.xxxx, x.xxxx)	0.xxx
Region (Asia vs. Europe)	x.xxx	(x.xxxx, x.xxxx)	0.xxx
Region (South America vs. Europe)	x.xxx	(x.xxxx, x.xxxx)	0.xxx
Age	x.xxx	(x.xxxx, x.xxxx)	0.xxx
GCS Motor Score (3 vs. 1/2)	x.xxx	(x.xxxx, x.xxxx)	0.xxx
GCS Motor Score (4 vs. 1/2)	x.xxx	(x.xxxx, x.xxxx)	0.xxx
GCS Motor Score (5/6 vs. 1/2)	x.xxx	(x.xxxx, x.xxxx)	0.xxx
Pupil Response (Bilateral vs. Unilateral/No Reactive Pupils/Not Testable)	x.xxx	(x.xxxx, x.xxxx)	0.xxx
CT Classification (I/II vs. V/VI)	x.xxx	(x.xxxx, x.xxxx)	0.xxx
CT Classification (III vs. V/VI)	x.xxx	(x.xxxx, x.xxxx)	0.xxx
CT Classification (IV vs. V/VI)	x.xxx	(x.xxxx, x.xxxx)	0.xxx

¹ For factors the last level is taken as the reference level. Marshall CT classification was used.

Source: Listings 16.2.6.1.6 and 16.2.6.3.1.

Program: xxxxxxx.sas, Output: xxxxxxx.rtf, Generated on: DDMONYYYY xx:xx, Page x of x

[Note to Programmer: Indicator variables or PROC TPHREG (which has a CLASS statement) will need to be created for the factors with more than 2 levels (Region, GCS motor score, Pupil Response and CT classification).

```

proc tphreg data=<dataset>;

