x-axis	Time (0-6/7 months)
x-axis (label)	Time (in months)
Legend (if applicable)	BHR-100, Placebo (different line type for each treatment group)
Footnote 1	Time to death = (Date of death or date of last contact (if censored) – date of TBI + 1)/30.4. Program: xxxxxxx.sas, Output: xxxxxxx.rtf, Generated on: DDMONYYYY xx:xx, Page x of x
Additional information	Censored observations should be identified. Output K-M survival estimates using OUTSURV on PROC LIFETEST statement or SURVIVAL statement. Then calculate 1-K-M survival estimates as want to calculate probability of death over time. Then multiply by 100 to obtain the percentage. Figure will run from 0% (no deaths) to 100% (all subjects have died) as the x-axis of time progresses from the left to the right. Figure corresponds with Table 14.2.5.5.

LISTINGS

Listing 16.2.1.1 Study Completion/Discontinuation Details

Treatment Group	Subject No.	Sex/ Age/ Race ¹	Infusion Administration Start Date/Time	Infusion Completion Date/Time	Completion Status	Reason for Early Termination (Specify)	Date of Study Completion/ Early Termination
BHR-100	xx-xxx	M/35/W		DDMONYYYY/ XX:XX	Completed	(Death, Adverse Event(s), Withdrawal of Consent, Protocol Violation, Lost to Follow-up, Discretion of the Investigator, Discretion of the Sponsor, other) (provide details when reason for termination is other)	DDMONYYYY
	xx-xxx	F/33/B		DDMONYYYY/ XX:XX	Withdrew	Other (xxxxxxxxxxxxxxxxxxxxxxxxxxxxxx)	DDMONYYYY
...							

¹ M = Male, F = Female; W = White, B = Black, African American or of African Heritage, P = Native Hawaiian or Other Pacific Islander, A = Asian, N = American Indian or Alaska Native, Z=Not Allowed to Obtain, O = Other.

Program: xxxxxxx.sas, Output: xxxxxxx.rtf, Generated on: DDMONYYYY xx:xx, Page x of x

Listing 16.2.1.2 Eligibility/Randomization

Treatment Group	Subject No.	Sex/ Age/ Race ¹	Date/Time of Written Informed Consent	Subject met all entry criteria?	Inclusion/Exclusion Criteria Not Met	Subject Randomized?	Date/Time of Randomization
BHR-100	xx-xxx	M/35/W	DDMONYYYY/ XX:XX	(Yes, No)	Inclusion Criteria 1	(Yes, No)	DDMONYYYY/ XX:XX

¹ M = Male, F = Female; W = White, B = Black, African American or of African Heritage, P = Native Hawaiian or Other Pacific Islander, A = Asian, N = American Indian or Alaska Native, Z=Not Allowed to Obtain, O = Other.

Program: xxxxxxx.sas, Output: xxxxxxx.rtf, Generated on: DDMONYYYY xx:xx, Page x of x

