¹ M = Male, F = Female; W = White, B = Black, African American or of African Heritage, P = Native Hawaiian or Other Pacific Islander, A = Asian, N = American Indian or Alaska Native, Z=Not Allowed to Obtain, O = Other.

Program: xxxxxxx.sas, Output: xxxxxxx.rtf, Generated on: DDMONYYYY xx:xx, Page x of x

Repeat this shell for

Listing 16.2.6.1.7 Primary Efficacy, Covariates, and Subgroup Variables (Missing Values Imputed)

Add

Note: Missing values are first imputed by carrying forward the Month 3 GOS assessment. If a subject has neither the 3 nor the 6 month GOS, the missing value is imputed based upon the primary proportional odds model. Missing covariates are imputed as the most common level over all subjects.

Listing 16.2.6.2 Sliding Dichotomy

Treatment Group	Subject No.	Sex/ Age/ Race ¹	Visit	Prognosis Group	GOS Group (4-level)	GOS Group (2-level)
BHR-100	xx-xxx	M/30/W	Month 6	(Best, Intermediate, Worst)	(Good Recovery, Moderate Disability, Severe Disability, Vegetative State/Dead)	(Favorable, Unfavorable)

¹ M = Male, F = Female; W = White, B = Black or African American, P = Native Hawaiian or Other Pacific Islander, A = Asian, N = American Indian or Alaska Native, O = Other.

Program: xxxxxxx.sas, Output: xxxxxxx.rtf, Generated on: DDMONYYYY xx:xx, Page x of x

Listing 16.2.6.3 Mortality

Treatment Group	Subject No.	Sex/ Age/ Race ¹	Visit	Status (If Other, Specify)	Patient Residence	Date of Death or Date of Last Contact	Time to Death or Last Contact (days) ²
BHR-100	xx-xxx	M/30/W	Month 1	(Lost to Follow-up, Consent Withdrawn, Alive, Dead, Other [specify])	(At Home, Hospital, Rehab Unit, Nursing Home/Long-Term Care, Other[Specify])	DDMONYYYY	XX*
			Month 6				

¹ M = Male, F = Female, W = White, B = Black or African American, P = Native Hawaiian or Other Pacific Islander, A = Asian, N = American Indian or Alaska Native, O = Other.

² If subject has not died, they will be censored on their last date of contact for the Kaplan-Meier survival analysis.

* Indicates that time to death or last contact is censored.

Program: xxxxxxx.sas, Output: xxxxxxx.rtf, Generated on: DDMONYYYY xx:xx, Page x of x

Listing 16.2.6.4.1 SF-36, Explanation of Categories

Question	Explanation
1. In general, would you say your health is:	1=Excellent, 2=Very Good, 3=Good, 4=Fair, 5=Poor.

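### The exploratory time-to-death analysis has two incompatible censoring rules, and most of its planned quantiles are not expected to be estimable at the design assumptions

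*SAP*

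**What the plan says.** **Censoring, SAP text.** For a subject who does not die, Section 5 (Time to death) says "they will be censored at the earliest (minimum) of their Month 6 GOS assessment date and end of study date". Section 9.5.3.1 agrees: "censored at their Month 6 GOS assessment or end of study date, whichever comes first". Section 5 adds a cut-off for late deaths: "subjects who have a death recorded after the assessment will be censored on the date of their Month 6 assessment". The SAP does not define the end of study date. The nearest item is the exit date in Listing 16.2.3.1, which is the date of completion or early termination.

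**Censoring, SAP shells.** The Table 14.2.5.5 footnote defines time to death as "Date of death/date of last contact (for censored records) - date of TBI + 1". The Figure 14.2.3.3 footnote starts from "Date of death or date of last contact (if censored" and converts to months. Listing 16.2.6.3 says "If subject has not died, they will be censored on their last date of contact for the Kaplan-Meier survival analysis".

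**Loss to follow-up.** Under Protocol Section 4.3 a subject is lost when he or she misses scheduled visits and "does not respond to multiple telephone or written attempts to contact".

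**Statistics to be reported.** Section 9.5.3.1 asks for "estimates of 25th, 50th, and 75th quartiles and corresponding 95% confidence limits of the median time to death", a log-rank test, a cumulative mortality plot and an adjusted Cox model. Table 14.2.5.5 shows deaths, censored counts, the three quantiles and the log-rank p-value. SAP Section 3.1 assumes 29% vegetative or dead at 6 months on placebo and a common odds ratio of 1.5.

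**The concern.** Text and shells give different censoring dates for one Kaplan-Meier and Cox analysis. SAP Section 10 requires independently programmed datasets to match fully, so the programmers will have to settle on one rule, and the SAP does not say which.

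The choice matters for subjects with no Month 6 GOS. For them the text rule reduces to the end of study date. If that date is later than the last contact, the interval between the two counts as observed survival although nobody saw the subject alive. Estimated mortality then falls, and falls unequally if losses differ by arm. The Month 1 and Month 6 Fisher tests omit subjects of unknown status, so this is the planned mortality analysis that uses a lost subject's partial follow-up.

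The second issue is what Table 14.2.5.5 would show. If well under half of each arm is expected to die, a median, its confidence interval and a 75th percentile say little. The table has no Kaplan-Meier mortality estimate at any fixed day.

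**Working it through.** **1. The two rules by type of subject**

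| Subject | SAP text | Shells | Same date? |
|---|---|---|---|
| Alive, Month 6 GOS done | Month 6 GOS date (end of study date if earlier) | Last contact | Yes, if that visit is the last contact |
| Death recorded after the Month 6 assessment | Censored at the assessment | Formula has no cut-off | No |
| No Month 6 GOS, lost to follow-up | End of study date | Last contact | Only if the site enters the last contact as the termination date |

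The shells carry the two dates separately: Listing 16.2.6.3 has a death or last-contact date, and Listing 16.2.1.1 has a completion or early-termination date.

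**2. Size of the censoring effect**

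The documents give no dropout rate, so the loss figures are assumptions. If lost subjects are carried as alive to about Day 180, mortality is understated by roughly (share lost) × (mortality between last contact and Day 180):

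- 3% lost, 5% later mortality: 0.03 × 0.05 = 0.15 points.
- 10% lost, 8% later mortality: 0.10 × 0.08 = 0.80 points.
- Termination date equal to last contact: 0.

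A simulation checked this with 590 per arm and 400 runs per setting. It assumed 80% of deaths in the first 30 days, last contact of lost subjects between Days 15 and 90, and their end of study date set to Day 180. Estimated Day-180 survival was:

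| Mortality | Loss | Text rule | Last contact | Difference (points) |
|---|---|---|---|---|
| 29% | 5% | 72.26% | 71.95% | 0.31 |
| 29% | 10% | 72.58% | 71.83% | 0.75 |
| 21.4% | 5% | 79.49% | 79.18% | 0.31 |
| 21.4% | 10% | 79.68% | 79.20% | 0.48 |

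The rules were run on separate random draws, so each difference has a Monte Carlo standard error of about √(2 × 0.29 × 0.71 / (590 × 400)) = 0.0013, or 0.13 points. Read the results as an order of magnitude: below 1 point.

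**3. Reproducing the sample size**

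Whitehead's formula is N = 12(z₀.₉₉₅ + z₀.₉₀)² / [(ln OR)² (1 − Σp̄ᵢ³)]. For 31/21/19/29 on placebo, OR 1.5 gives 40.26/21.65/16.69/21.40 on BHR-100. The mean proportions are 0.356, 0.213, 0.178 and 0.252, and 1 − Σp̄³ = 0.923. Then N = 12 × 3.857² / (0.1644 × 0.923) ≈ 1176, against 1180 stated. The plan's inputs are therefore read correctly.

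**4. Highest mortality these inputs allow**

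- Placebo: all 29% dead, 0.29 × 590 ≈ 171 deaths.
- BHR-100: odds of a better outcome are (0.71/0.29) × 1.5 = 3.672, so vegetative or dead is 1/4.672 = 21.4%, and 0.214 × 590 ≈ 126 deaths.

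**5. Deaths needed for each quantile (crude count, 590 per arm)**

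| Quantile | Deaths needed | P at 29% | P at 21.4% |
|---|---|---|---|
| 25th | 148 | 0.985 | 0.018 |
| Median | 295 | 8 × 10⁻²⁷ | 8 × 10⁻⁵³ |
| 75th | 443 | 3 × 10⁻¹¹⁸ | 3 × 10⁻¹⁷⁰ |

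Because 29% includes vegetative subjects, placebo mortality may be lower: the 25th percentile is reached with probability 0.86 at 27% and 0.50 at 25%. At 39%, the highest mortality cited in Protocol Section 1.1, the chance of reaching the median is still 4 × 10⁻⁸. In the simulation the curve fell to 50% in 0 to about 1% of arms, when a late death occurred with few subjects still at risk.

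**The case against.** The strongest reply is that the survival credit is not established. A reader might infer that the text rule certainly counts survival after last contact. The documents do not support that: Protocol Section 4.3 sets a criterion for declaring loss, not a rule for dating it, and the end of study date is undefined. If sites enter the last contact, the rules coincide for lost subjects. Few subjects should be affected in any case, since both documents expect minimal missing data. This stands, and it is why the effect range starts at zero. The conflict between text and shells remains.

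A reader might also infer that the quantiles cannot be reached. That is too strong. At 29% mortality the 25th percentile is likely on placebo, and in both arms if there is no effect. At 39% on placebo, OR 1.5 gives odds of (0.39/0.61)/1.5 = 0.426, or about 30% on BHR-100, and the 25th is reached in both arms. The median and 75th percentile are not expected, though not strictly impossible.

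Nor would Table 14.2.5.5 be empty. It keeps deaths, censored counts and the log-rank p-value. The plot and Cox hazard ratio are planned, as are crude Month 1 and Month 6 mortality differences with 95% CIs (Section 9.5.2.1). An unreached quantile does not bias any of these. What is missing is a Kaplan-Meier estimate with a CI at a fixed day, which, unlike the crude proportions, uses lost subjects' partial follow-up.

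Finally, last contact is not free of bias. Section 9.5.2.1 promises every effort to ascertain survival status. Counting deaths learned of after contact was lost, while censoring survivors at last contact, would push mortality up.

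**Conclusion.** The point holds as a minor one. The SAP's text and its table, figure and listing shells give incompatible censoring rules for time to death. They can differ for subjects without a Month 6 GOS and for deaths recorded after the Month 6 assessment. For lost subjects the text rule may overstate survival, by between zero and about 0.8 points at Day 180. The upper end rests on an assumed 10% loss and on termination dates near Day 180; neither is in the documents.

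At the design assumptions, the median with its CI and the 75th percentile are not expected in either arm, nor the 25th percentile on BHR-100 at OR 1.5. That makes five of the six planned quantiles. The log-rank, Cox and Fisher results are unaffected by the quantile problem; the censoring rule touches only the Kaplan-Meier, log-rank and Cox results.

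A reader might infer that the trial's mortality conclusions are at risk. They are not. Section 9.5.3 makes time to death exploratory, and Section 9 treats such analyses as supportive. The ranked mortality endpoints use Fisher's exact test, which does not use this censoring date. No primary or ranked secondary conclusion changes.

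**What to change.** 1. State one rule in Sections 5 and 9.5.3.1 and in the notes to Table 14.2.5.5, Figure 14.2.3.3 and Listing 16.2.6.3: censor at the Month 6 GOS date or, if there is none, at the last date known alive from any vital-status source. This removes the undefined end of study date from the rule.
2. Keep the existing cut-off for deaths after the Month 6 assessment, and repeat it in the shells.
3. In Table 14.2.5.5, replace the median (with its CI) and the 75th percentile by Kaplan-Meier mortality at Days 30, 90 and 180 with 95% CIs and the between-arm difference. The 25th percentile can stay.

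The cost is SAP wording and one table shell. There is a small risk of upward bias if late-reported deaths are counted while survivors are censored at an old contact date. Updating the last-known-alive date from the same sources that supply the deaths limits it.

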6 ANALYSIS SETS

The following analysis populations will be defined for this study:

- Modified Intention-to-treat (mITT),
- Per Protocol (PP), and
- Safety.

The assignment of subjects to the study populations will occur at the blinded review meeting which will encompass discussion of major protocol violations.

